5.6 Evaluable for Cycle Control Analysis Population

Evaluable for Cycle Control (ECYC) analysis population will include only those safety subjects with at least one cycle for which: A) a pregnancy did not occur; and B) there is bleeding related e-diary data.

6 Analysis Methods

6.1 General Methodology

Analyses will be implemented using SAS® 9.4 or above. In general, all efficacy and safety variables will be summarised using descriptive statistics and graphs as appropriate. Continuous variables will be summarised by descriptive statistics (sample size (n), mean, standard deviation (SD), minimum, median, and maximum). Categorical variables will be summarised in frequency tables (frequencies and percentages). Time to event variables will be summarised by Kaplan-Meier estimates of median and quartile time to events. Individual data will be presented in subject listings.

Means and medians will be displayed with one more decimal place than the collected data, and SDs will have one more decimal place than the means and medians. Minimum and maximum will be displayed with the same number of decimal places as the collected data. Percentages will be rounded to one decimal place.

No formal statistical testing will be performed on subject disposition, demographic, baseline characteristic, and safety data. Where appropriate, point estimates, together with their 95% confidence intervals will be presented.

Only observed data, with no data imputation, will be used for the efficacy analyses unless otherwise specified. Safety analyses will also be conducted on the observed data. However, for the start date/time of an AE or medication being partially or completely missing, the worst case scenario will be applied. That is, the AE will be assumed to be treatment emergent, and the medication will be considered to be concomitant.

6.2 Analysis Methods

6.2.1 Patient Disposition and Withdrawals

The number and percentage of screen failure, subjects enrolled, subjects with study device successfully deployed, discontinued 1-Year study prematurely, completed 1-year study, reason for discontinuation of 1-year study, entered the extension study, discontinued extension study prematurely, completed extension study, reason for discontinuation of extension study will be presented. Selected information will also be summarized by site.

The number and percentage of subjects at each scheduled visit will be presented.

The number and percentage of subjects in each population will be presented.

Details of all subjects who violated the inclusion/exclusion criteria will be listed.

A listing will be presented to describe site number, date of study device placement, study completion or discontinuation, and primary reason for existing study for each screened subject.

6.2.2 Demographic and Baseline Characteristics

Demographic and other baseline characteristics, such as age at date of informed consent, age groups, ethnicity, race, marital status, parity status, weight, height, and body mass index (BMI) at baseline as well as uterine length will be summarised for all enrolled subjects.

Age will be categorized by two groups, 18 - 35 and 36 - 40 years.

BMI will be categorized by Underweight (< 18.5), Normal (18.5 – 24.9), Overweight (25.0 – 29.9), and Obese (≥ 30.0).

All demographic and baseline characteristics will be presented in a data listing.

6.2.3 Medical / Surgical History

Medical / Surgical history will be summarized given the number and percentage by body system for the safety population. Subject reporting the same body system multiple times will be counted only once for that body system.

All history will be presented in a data listing.

6.2.4 Gynecological History

Gynecological history data will be summarized for all questions collected on the CRF.

All gynecological history will be presented in a data listing.

6.2.5 Menstrual History

Menstrual history data will be summarized for all questions collected on the CRF.

All menstrual history will be presented in a data listing.

6.2.6 Cervical Cytology

Cervical cytology test results will be summarized in table and presented in a data listing.

6.2.9 Safety Variables

All safety analyses will be based on safety analysis population unless otherwise specified. Descriptive statistics will be used to summarise the safety outcomes. No inferential analyses of safety data are planned.

6.2.9.1 Adverse Events

Number of AEs will be summarised by SOC and/or PT for the following categories of TEAEs: all AEs, SAEs, AEs related to study device, AEs related to study device placement/removal procedure, AEs leading to death, AEs leading to study device removal and AEs as primary reason for exiting study. Patients with more than one occurrence of the same SOC (PT) will be counted only once within the SOC (PT) categorisation.

AEs will also be summarised similarly by severity (i.e. mild, moderate, severe), relationship to study device (i.e. not related, unlikely related, probably related, related), relationship to placement/removal procedure (i.e. not related, unlikely related, probably related, related) and onset time frame (i.e. 0-3 months, >3-6 months, >6-12 months, >12 months). Should a subject experience more than one occurrence of the same SOC (PT), the subject's worst occurrence (worst intensity/most related causality) will be retained in the tabulation.

All AEs, including AEs that started prior to the study device placement, will be presented in data listings. In addition, separate listings of all SAEs, AEs related to study device, AEs related to study device placement/removal procedure, AEs leading to death, AEs leading to study device removal and AEs as primary reason for exiting study will be provided. In case of any AEs reported from study device insertion failure subjects, selected AE tables will be repeated for all enrolled subjects for all AEs.

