### **Adverse Events**

The number and percentage of subjects with each adverse event and serious adverse event will be presented in a table by MedDRA system-organ class and preferred term. Summaries will also be presented by relationship to the LevoCept placement or removal procedure and the severity of the adverse event. All adverse events will be summarized with special attention to those events that may be related to an intrauterine contraceptive, including:

- Acne
- Amenorrhea
- Back pain
- Breast cancer
- Breast tenderness
- Depression/depressive mood
- Dysmenorrhea
- Dyspareunia
- Ectopic pregnancy
- Embedment
- Expulsion, partial or complete
- Headache, migraine
- Intrauterine pregnancy
- Irregular menstrual bleeding
- Leukorrhea
- Ovarian cysts
- Pain and cramping
- Pelvic infection
- Perforation
- Sepsis
- Vaginitis
- Vasovagal reaction immediately after placement

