6.2.9.7 Device Expulsion and Removal

Device expulsion will be recorded daily by the subject in e-diary. Device removal procedure will be recorded in the CRF. Cumulative study device removal rates and expulsion rates will be summarized at 1-year (study day 1 - 364), 2-year (study day 365 - 728), and 3-year (study day 729 +).

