8.1 Changes in the Conduct of the Study

8.2 Changes to the Planned Analyses

- In the protocol, safety and enrolled subjects are defined as the same, all enrolled subjects who underwent the study device placement procedure, regardless of whether the study device was successfully placed or not. In this analysis plan, the safety analysis population will include all enrolled subjects who underwent a successful study device placement procedure.
- In the protocol, pre-treatment and on-treatment subjects are not specified in EP analysis population. In this analysis plan, pre-treatment subjects are excluded from EP.

9 SAS Data Transfer

All SAS reported study data will be transferred to Sebela and will be performed in compliance with CDISC (Clinical Data Interchange Standards Consortium) on issue of the final draft clinical study report (CSR). Synteract will provide metadata files along with the clinical and efficacy data.

All study data will be transferred as SAS transport files in standard SDTM/ADaM (Study Data Tabulation Model/Analysis Data Model) dataset format.

10 Reporting Conventions

The following reporting conventions will be adopted for the presentation of study data. These conventions will enhance the review process and help to standardise presentation with common notations.

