	14.3.1.10	Treatment-Emergent Adverse Events by System Organ Class and Preferred Term and by Relatedness to Study Device Placement/Removal Procedure (Safety Population)
	14.3.1.11	Treatment-Emergent Adverse Events by Preferred Term (Safety Population)
	14.3.1.12	Treatment-Emergent Adverse Events by Preferred Term by Onset Time Frame for the First Year (Safety Population)
	14.3.1.13	Treatment-Emergent Adverse Events by Preferred Term by Onset Time Frame (Safety Population)
14.3.2		Listings of Deaths, Other Serious and Significant Adverse Events
	14.3.2.1	Deaths (All Enrolled Subjects)

CONFIDENTIAL

ICH Heading	Table Number	Table Description
	14.3.2.2	Serious Adverse Events (All Enrolled Subjects)
	14.3.2.3	Adverse Events as Primary Reason for Exiting Study (All Enrolled Subjects)
14.3.5		Exposure
	14.3.5.1	Treatment Exposure (All Enrolled Subjects)
	14.3.5.2	Device Placement and Subject Pain During the Procedure (All Enrolled Subjects)
	14.3.5.3	Device Expulsion/Removal and Subject Pain During the Procedure (Safety Population)
	14.3.5.4	Transvaginal Ultrasound (Safety Population)
14.3.6		Individual Patient-Reported Outcome Measurements
	14.3.6.1.1	Bleeding and Spotting by Cycle (Safety Population)
	14.3.6.1.2	Bleeding and Spotting by Cycle (ECYC Population)
	14.3.6.2.1	Occurrence and Severity of Dyspareunia in Number of Days by Cycle (Safety Population)
	14.3.6.2.2	Occurrence and Severity of Dyspareunia in Number of Days by Cycle (ECYC Population)
	14.3.6.2.3	Occurrence and Severity of Dyspareunia – Worst Pain Grade Shift from Baseline by Cycle (Safety Population)
	14.3.6.2.4	Occurrence and Severity of Dyspareunia – Worst Pain Grade Shift from Baseline by Cycle (ECYC Subjects)
	14.3.6.2.5	Occurrence and Severity of Dyspareunia – Highest Frequency of Occurrence Pain Grade Shift from Baseline by Cycle (Safety Population)
	14.3.6.2.6	Occurrence and Severity of Dyspareunia – Highest Frequency of Occurrence Pain Grade Shift from Baseline by Cycle (ECYC Subjects)
	14.3.6.3.1	Occurrence and Severity of Menstrual Pain or Cramping in Number of Days by Cycle (Safety Population)
	14.3.6.3.2	Occurrence and Severity of Menstrual Pain or Cramping in Number of Days by Cycle (ECYC Population)
	14.3.6.3.3	Occurrence and Severity of Menstrual Pain or Cramping by Cycle (Safety Population)
	14.3.6.3.4	Occurrence and Severity of Menstrual Pain or Cramping by Cycle (ECYC Population)
14.3.7		Vital Signs and Other Data

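### The protocol singles out 22 IUD-related adverse events, but the SAP has no summary of them: about 14 appear only as SOC/PT rows, with no term grouping and no confidence interval

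*SAP*

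**What the plan says.** Protocol 20.7, under Adverse Events, first asks for a table of AEs and serious AEs by system organ class (SOC) and preferred term (PT). It then adds: "All adverse events will be summarized with special attention to those events that may be related to an intrauterine contraceptive, including", followed by 22 bullets that run from acne to "Vasovagal reaction immediately after placement". The same list stands in protocol 6.2 as the known harms of the marketed 52 mg device, with the statement that no difference in their severity or frequency is expected. The opening paragraph of protocol 20.7 also promises confidence intervals to help interpret the safety rates.

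SAP 6.2.9.1 says: "Number of AEs will be summarised by SOC and/or PT for the following categories of TEAEs". Its further breakdowns keep the same rows: "AEs will also be summarised similarly by severity (i.e. mild, moderate, severe), relationship to study device", then relationship to the procedure and time of onset. The counting rule is: "Patients with more than one occurrence of the same SOC (PT) will be counted only once within the SOC (PT) categorisation".

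SAP 8.2 records two departures from the protocol. One is the safety population ("In this analysis plan, the safety analysis population will include all enrolled subjects who underwent a successful study device placement procedure"); the other is the exclusion of pre-treatment pregnancies from the EP population. Neither concerns the list of 22.

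**The concern.** The protocol makes two promises about AEs: a full SOC/PT table, and particular attention to a named set. The SAP carries out the first and is silent on the second. The listed items are clinical concepts rather than coding terms; two of them, depression/depressive mood and headache/migraine, join two terms in one bullet. A SOC/PT table counts a woman once per row, and no rule counts her once per listed event.

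The study's stated purpose is to gather safety and effectiveness data to support a Phase III study. For the harms that the protocol itself regards as typical of this kind of product, a reader will want to know how many women had each one, and how precisely that is known. If the grouping of terms is left until the data are seen, the choice of terms can also follow the results.

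**Working it through.** There is no planned figure to reproduce, so the check sets the list against the SAP text, table index and shells, and then looks at what the rows can yield.

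**1. Coverage of the 22 events**

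| Where the SAP covers it | Events | Count |
|---|---|---|
| Own summary outside the AE tables | Expulsion (6.2.9.7, Table 14.3.5.3); dyspareunia (6.2.9.5); dysmenorrhea, and pain and cramping (6.2.9.4) | 4 |
| Indirectly | Amenorrhea and irregular bleeding, as days per cycle (6.2.9.6); intrauterine and ectopic pregnancy, not separated in the Pearl Index (4.1, Table 14.2.1) | 4 |
| SOC/PT rows only | Acne, back pain, breast cancer, breast tenderness, depression/depressive mood, embedment, headache/migraine, leukorrhea, ovarian cysts, pelvic infection, perforation, sepsis, vaginitis, vasovagal reaction | 14 |

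The total is 4 + 4 + 14 = 22. The sorting gives the SAP credit for indirect cover. Without that credit the last group would be 14 + 4 = 18.

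For expulsion the SAP is explicit: "Cumulative study device removal rates and expulsion rates will be summarized at 1-year", and again at two and three years. The diary summaries give days or pain grade per cycle. They do not give the number of women affected over the study, or relatedness.

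**2. What SOC/PT rows yield for one listed event**

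If the event is coded to a single PT, Table 14.3.1.11 already gives subjects n (%), and nothing is lost.

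If it is coded to several PTs, let the rows hold k1, k2, … women. The number of different women, W, then satisfies

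largest ki ≤ W ≤ sum of the ki.

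The upper limit is reached only when no woman has two of the terms. The SOC row does not settle W, because it pools other events, and one concept may fall in more than one SOC.

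Illustration. The AE counts and the split are assumed, since the documents give none. N = 250 is the planned enrollment; the SAP safety population would be smaller if placements fail. Take four PT rows of 3 women each, with exact (Clopper-Pearson) 95% intervals:

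- Each row: 3/250 = 1.2% (0.25 to 3.47).
- No overlap: W = 3 + 3 + 3 + 3 = 12, and 12/250 = 4.8% (2.50 to 8.23). The rows add up correctly.
- Eight different women: 8/250 = 3.2% (1.39 to 6.21). The rows still sum to 4.8%.
- Complete overlap: W = 3, and 3/250 = 1.2%.

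The same four printed rows thus fit any rate from 1.2% to 4.8%.

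**3. Confidence intervals**

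Protocol 20.7 promises intervals for safety rates. SAP 6.1 allows 95% intervals where appropriate, and SAP 6.2.9 plans no inferential safety analysis. A descriptive interval is compatible with both, yet none of the AE table shells has a column for one.

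**The case against.** **The protocol asks for SOC and PT, and the SAP delivers that.** This is true of the opening sentence of the AE paragraph. Special attention is not defined, and could be given in the text of the report; the protocol does not literally promise a separate table or grouped terms. What stands is that the commitment is vague. But a SAP is where a vague commitment is made definite, and this one does not mention the list at all. The promise of intervals is not vague.

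**Many of these harms do have rates.** This also stands. A reader might infer that no rate is produced for any known device harm. The documents do not support that: expulsion has cumulative rates, placement and removal pain have subject counts (6.2.9.3), menstrual pain, dyspareunia and bleeding have summaries by cycle, and single-term events have n (%). Pain in particular would be a poor example of the gap.

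**Splitting over several terms is conjecture.** A reader might infer that pelvic infection and similar harms will be scattered over many lines. Nothing in the documents shows how the verbatim terms will be coded. It is a risk, not a finding.

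**The information is not lost.** Listing 16.2.7.1 shows SOC, PT and verbatim text for each subject, and the datasets go to the sponsor, so a grouped count can be made later. That is right. What is missing is a planned count with its terms fixed in advance.

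**There is nothing to compare with.** Protocol 6.2 states an expectation about the marketed device, but neither document gives its rates or plans a comparison. The case for the table therefore rests on describing this study's own harms, not on a comparison.

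**Conclusion.** The point holds as an unmet reporting commitment of moderate weight. The SAP neither carries out nor withdraws the protocol's focused summary of 22 events, and its AE shells lack the promised intervals. Those two statements need no assumption. About 14 of the 22 rest on SOC/PT rows alone; that figure depends on how indirect cover is classed. The possible distortion of a rate is conditional on two things: the event being coded to more than one PT, and some women having more than one of those terms. Its size cannot be known from the documents, and the 1.2% to 4.8% range is an illustration only. The primary Pearl Index is untouched, and no data would be lost. This is a cheap improvement rather than a defect that endangers the study.

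**What to change.** Add one table of treatment-emergent AEs to SAP 6.2.9.1 for the events listed in protocol 20.7:

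- Define each event by a list of preferred terms fixed before database lock. Section 7 of the SAP plans the same analyses for the one-year report, so the lock for that report is the one that counts.
- Count each woman once per event, and give n (%) with an exact 95% CI, overall and for events judged probably related or related.
- For expulsion, refer to Table 14.3.5.3 rather than repeat it. For intrauterine pregnancy, refer to the pregnancy data, because protocol 15.2 treats pregnancy as an outcome and not an AE. Take ectopic pregnancy from the AE data, because protocol 15.1 makes it a serious AE.

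If the sponsor prefers not to add the table, SAP 8.2 should record the omission and the reason. The cost is one term-mapping list and one extra table, both from data already collected and coded. No endpoint, visit or clinical rule changes.

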6.2.9.2 Extent of Exposure

The number of subjects with study device deployed and number of cycles of use to the study device will be summarized in enrolled subjects regardless of whether the study device was successfully placed or not. For subjects without successful placement, the number of cycles of use for the study device will be zero.

6.2.9.3 Device Placement & Removal, Subject Pain

The ease of study device placement and removal, subject pain, medication, as well as insertions requiring cervical dilation during the procedure, will be summarized categorically with number and percentages of subjects in each category for all enrolled subjects.

All device placement and removal data will be presented in data listings.

6.2.9.4 Device Subject Discomfort

Experience of any menstrual pain or cramping will be recorded daily by the subject in the e-diary. The occurrence and severity of discomfort will be summarized for each cycle in safety and ECYC population. The summary will present the number of days, the worst pain grade and the highest frequency occurrence pain grade in each cycle with menstrual pain or cramping.

If a cycle has less than 28 days but at least 14 days data, missing value will be imputed by the average in the same cycle for the subject, and then rounded to nearest integer.

For example, a subject at Cycle 6 has only 20 days data, of which 3 days with "Cramping". Total number of "Cramping" days at this cycle for her will be estimated as:

$$3 + (3 / 20 \times (28 - 20)),$$

which will be 4 after rounding.

If a cycle has less than 14 days data, no imputation for missing value, number of days for this cycle would be treated as missing.

All device subject discomfort e-diary data will be presented in data listings.

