6.2.9.6 Bleeding and Spotting

Vaginal bleeding and spotting will be recorded daily by subjects in e-diary. The total number of bleeding or spotting days will be summarized for each cycle in safety and ECYC population. The missing value imputation at cycles will be calculated similarly as the above Section 6.2.9.4.

In addition, bleeding and spotting will be summarized separately (i.e. none, spotting, light bleeding, medium bleeding, heavy bleeding). Subjects who discontinue the study due to bleeding complaints prior to completing one 28-day cycle will be included in the bleeding analysis.

When bleeding occurred, flows heavier than when not using hormones will also be summarized by cycle.

All bleed and spotting e-diary data will be presented in data listings.

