Reference: Listing xxx.

Program Location: \\xx\xxx\xxx\xxx\xxxxxx\xxxxxxxxxxxxxxxxxxxx\xxxx\xxxxx.sas

date

time

Table 14.3.5.4
Transvaginal Ultrasound (Safety Population)

	All Subjects (N=xx)
Device in Place	
n	n (%)
Yes	n (%)
No	n (%)

Reference: Listing xxx.

Program Location: \\xx\xxx\xxx\xxx\xxxxxx\xxxxxxxxxxxxxxxx\xxxx\xxxxx.sas date time

CONFIDENTIAL

Sebela Pharmaceuticals Development LLC
CMDOC-0022

Page x of y

Table 14.3.6.1.1
Bleeding and Spotting by Cycle (Safety Population)

Number of Days With	Cycle Statistic	All Subjects (N=xx)
Bleeding or Spotting	Cycle 1	
	n	xx
	Mean	xx.x
	SD	xx.xx
	Median	xx.x
	Min	xx
	Max	xx
	xxxxx	
	n	xx
	Mean	xx.x
	SD	xx.xx
	Median	xx.x
	Min	xx
	Max	xx
None		
Spotting		
Light Bleeding		
Medium Bleeding		
Heavy Bleeding		
Bleeding		
Heavier Flow than when not Using Hormones		
Heavier Flow than when not Using Hormones when Bleeding occurred		

CONFIDENTIAL

Note: Bleeding include Light Bleeding, Medium Bleeding and Heavy Bleeding.

Note: Menses question has the following choices: None, Spotting (minimal bleeding, no sanitary products required), Light Bleeding (pad, liner, or tampon used), Medium Bleeding (pad, liner, or tampon used), Heavy Bleeding (pad, liner, or tampon used).

Note: The heavy flow question is only asked when the subject responds with Spotting, Light Bleeding, Medium Bleeding, or Heavy Bleeding to the menses question.

Reference: Listing xxx.

Program Location: \\xx\xxx\xxx\xxx\xxxxxx\xxxxxxxxxxxxxxxxxxxx\xxxx\xxxxx.sas

date

time

Programmer note:

1. Table will continue with all cycles and remaining symptom.

2. Follow a similar format as Table 16.3.6.1.1 for:

Table 16.3.6.1.2 Bleeding and Spotting by Cycle (ECYC Population)

CONFIDENTIAL

Sebela Pharmaceuticals Development LLC
CMDOC-0022

Page x of y

Table 14.3.6.2.1
Occurrence and Severity of Dyspareunia in Number of Days by Cycle (Safety Population)

Cycle Statistic	All Subjects (N=xx)					
	No Pain	Some Pain	Painful	Moderately Painful	Very Painful	Not Applicable
Cycle 1						
n	xx	xx	xx	xx	xx	xx
Mean	xx.x	xx.x	xx.x	xx.x	xx.x	xx.x
SD	xx.xx	xx.xx	xx.xx	xx.xx	xx.xx	xx.xx
Median	xx.x	xx.x	xx.x	xx.x	xx.x	xx.x
Min	xx	xx	xx	xx	xx	xx
Max	xx	xx	xx	xx	xx	xx
xxxxx						
n	xx	xx	xx	xx	xx	xx
Mean	xx.x	xx.x	xx.x	xx.x	xx.x	xx.x
SD	xx.xx	xx.xx	xx.xx	xx.xx	xx.xx	xx.xx
Median	xx.x	xx.x	xx.x	xx.x	xx.x	xx.x
Min	xx	xx	xx	xx	xx	xx
Max	xx	xx	xx	xx	xx	xx

Reference: Listing xxx.

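### Rounding imputed diary day counts to whole numbers cancels the imputation for one-day counts at 19 to 27 recorded days, over-imputes them at 15 to 18, and can leave bleeding categories that do not add to their totals

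*SAP*

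**What the plan says.** SAP 6.2.9.4 (Device Subject Discomfort) sets the rule for cramping days. It applies "If a cycle has less than 28 days but at least 14 days data": the "missing value will be imputed by the average in the same cycle for the subject, and then rounded to nearest integer". The worked example takes a case where "a subject at Cycle 6 has only 20 days data, of which 3 days with" cramping, adds the average for the eight missing days, and gives a result "which will be 4 after rounding". Below the threshold the count is left missing: "If a cycle has less than 14 days data, no imputation for missing value".

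Section 6.2.9.6 extends the rule to bleeding: "The missing value imputation at cycles will be calculated similarly as the above Section 6.2.9.4". Section 6.2.9.5 does the same for dyspareunia.

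The shell for Table 14.3.6.1.1 has rows for none, spotting, light, medium and heavy bleeding, plus *Bleeding or Spotting* and *Bleeding*. Its footnote reads "Bleeding include Light Bleeding, Medium Bleeding and Heavy Bleeding". The cramping shell, Table 14.3.6.3.1, has columns for none, mild, moderate and severe, and no total. On precision, SAP 6.1 states: "Means and medians will be displayed with one more decimal place than the collected data".

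**The concern.** The imputation is meant to put incomplete cycles on a 28-day footing, so that a day count does not depend on how many diary entries were made. Rounding each cycle's result to a whole number partly undoes this. When the count is small, the increment for the missing days is often below half a day and is dropped; in other cycles it is rounded up to a full day. The result then moves in steps with diary completeness.

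Counts in the heavier or more severe grades are likely to be small, so they are the most exposed. Bleeding and spotting pattern is a named tolerability outcome in protocol 5.2. A second consequence is that separately rounded categories may disagree with a total shown in the same table.

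**Working it through.** **Inputs.** d is the number of recorded days, 14 to 27 (SAP 6.2.9.4). k is the number of those days with the symptom. The imputed count is k + (k/d)(28 − d) = 28k/d, then rounded.

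**The plan's own figure.** With k = 3 and d = 20: 3 + (3/20) × 8 = 4.2, which rounds to 4. This matches the SAP. Rounding the daily average first would give 3 + 0 × 8 = 3, so the example rules that reading out.

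**One-day counts (k = 1).**

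| d | 28/d | Rounded | Error against 28/d |
|---|---|---|---|
| 27 | 1.04 | 1 | −3.6% |
| 24 | 1.17 | 1 | −14% |
| 20 | 1.40 | 1 | −29% |
| 19 | 1.47 | 1 | −32% |
| 18 | 1.56 | 2 | +29% |
| 15 | 1.87 | 2 | +7% |
| 14 | 2.00 | 2 | 0 |

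The result is 1, so nothing is imputed, at all nine values from 19 to 27. It is too high at the four values from 15 to 18 and exact at 14.

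**Larger counts.** At d = 27 the increment is k/27, which is below 0.5 for k up to 13 (13 × 28/27 = 13.48), so no count up to 13 changes. At d = 26 the same holds up to k = 6 (6 × 28/26 = 6.46).

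**Expected effect on a rare grade.** Assume the grade occurs on 1% of days, independently, so the true mean is 28 × 0.01 = 0.28 days per cycle. Taking k as Binomial(d, 0.01), the expected rounded count is:

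- d = 27: 0.270 (−0.01 days)
- d = 24: 0.242 (−0.04)
- d = 20: 0.217 (−0.06)
- d = 19: 0.205 (−0.07)
- d = 18: 0.346 (+0.07)
- d = 15: 0.300 (+0.02)

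With equal weight on each d, the net bias is −15% over 19 to 27 days but only −5% over 14 to 27. For a common outcome (25% of days, 7 days per cycle) the error is at most about 3.5% at any d.

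**Dependence on missingness.** The documents give no pattern of missed diary days. Assume instead that days are missing completely at random and that the true count is one day. Among incomplete cycles that are imputed:

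| Days missing | Share with d ≥ 19 | Net bias |
|---|---|---|
| 5% | 100% | −6.6% |
| 10% | 100% | −10.5% |
| 20% | 96% | −17.6% |
| 30% | 69% | −10.9% |
| 40% | 29% | +3.1% |

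**Additivity, if the rule runs on each grade.** Take one day each of spotting, light, medium and heavy bleeding.

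- d = 20: each category is 1.4, rounded to 1, so the four sum to 4. The total is 4 × 1.4 = 5.6, rounded to 6.
- d = 18: each category is 1.56, rounded to 2, so the four sum to 8. The total is 4 × 28/18 = 6.22, rounded to 6.

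Without rounding, the categories add exactly to the total, and all five rows including none add to 28.

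**The case against.** A reader might infer that the plan systematically understates heavy bleeding and severe cramping. The documents do not support that. One-day counts are too high at 15 to 18 recorded days, the net bias turns positive when about 40% of days are missing, and no missingness pattern is given. Nor is there a clean contrast between rare and common grades: at d = 27 the error is −3.6% for a 1% grade and −3.5% for a 7-day outcome. This objection stands, and the direction of any bias must be stated conditionally.

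Per-grade application is an inference. The worked example scales cramping as a whole, and in 6.2.9.6 the imputation sentence follows the total, before the separate categories are introduced. The shells make per-grade use the natural reading, but the text does not say so. If only totals were imputed, categories left unscaled would still not generally add to them, so the scope needs stating either way. The cramping shell shows no total, so the visible mismatch is confined to the bleeding table.

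Severe pain is also reported by another route. The worst-grade tables for cramping and dyspareunia count a single severe day in full, and raw diary data are listed. Missed dyspareunia entries can also be recovered at monthly contact. This stands for pain; bleeding has no worst-grade table.

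Whole-day values do serve one purpose: SAP 6.1 shows minimum and maximum with the decimals of the collected data. That is a reason to round at display. It does not require rounding each cycle's value before means are taken.

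**Conclusion.** The point holds as a minor improvement. It is certain, from the SAP's formula alone, that rounding cancels the imputation for one-day counts at 19 to 27 recorded days, cancels it for every count up to 13 at 27 days, and over-imputes one-day counts by 7% to 29% at 15 to 18 days. Net understatement of rare grades depends on most incomplete cycles missing nine days or fewer, which is plausible but not shown. Even then it amounts to hundredths of a day per incomplete cycle for a grade on an assumed 1% of days, and complete cycles dilute it further, so much of it would not show in a mean given to one decimal.

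Non-additivity in Table 14.3.6.1.1 depends on per-grade application. Categories can then fall short of or exceed their total; they need not disagree in every cycle. The tables concerned are descriptive. The Pearl Index does not use these counts, and the worst-grade tables are unaffected because the SAP describes imputation for numbers of days.

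**What to change.** In SAP 6.2.9.4, delete the rounding clause that ends the imputation sentence and carry 28k/d unrounded, rounding only for display. The worked example becomes 4.2. State that the rule applies to each grade, and derive *Bleeding* and *Bleeding or Spotting* as sums of the unrounded categories. Make the same change where 6.2.9.5 and 6.2.9.6 refer back to the rule.

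The cost is a small wording change and a small change in the derivation program. The one drawback is that the minimum and maximum for imputed cycles may be non-integer, so the SAP must either allow a decimal there or say that they are rounded at display.
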